9.2 RANDOMISATION (Visit 2)

Subjects will be registered into the study at the Screening visit and assigned a unique subject identification number in the IRT. Subjects will be categorised during the screening process based upon their age (2 to \leq 9 years of age and 10 to \leq 17 years of age) and their gender. Age and gender will be incorporated into the randomisation as stratification factors. A minimum of 18 subjects must be recruited into the 2-9 and 10-17 age group and a minimum of 25% of either sex must be recruited. Maximum of 12 subjects will be recruited in the 1 m - 2 yrs cohort. In the event of a subject having a birthday whilst on study and they move to a different age cohort -they will remain in the baseline cohort for the duration of the study.

A final eligibility evaluation must be conducted by the Investigator/designee prior to randomisation/pre-assignment PK visit via IRT, once the results of all Screening assessments are available.

Subjects aged 1 month to < 2 years:

Following the eligibility evaluation, a maximum of 12 subjects will enter a Pre-assignment phase: 1-day Pharmacokinetic assessment day following a single dose of 0.1 ml/kg ferric maltol oral suspension. Once the PK samples have been analysed and evidence is showing metabolism and elimination of maltol, subjects will be assigned to ferric maltol oral suspension treatment phase. Subjects will be eligible to enter the treatment phase if their maltol level returns to baseline, or to a level confirming there is no accumulation of maltol

CONFIDENTIAL Page 52 of 80

or maltol glucuronide. The sample results will be analysed on an individual basis. The Sponsor's Medical Monitor will make a recommendation to the investigator based on preassignment results. The investigator will make the final decision if subjects aged 1 month to < 2 years are eligible to enter the treatment phase.

Subjects aged 2 years to 17 years:

No subject may begin treatment prior to being randomised in the IRT. The randomisation procedure (created using a computer-generated random permutation procedure) will assign the subject to one of the treatment arms.

Initial dosing with ferric maltol and ferrous sulfate must occur on the same day of randomisation. The date of Visit 2 is the date of first dose with ferric maltol or ferrous sulfate.

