- 6. Pre-assignment phase: All subjects in 1 m-< 2 yrs age group will enter a 1-day PK assessment day prior to entering the treatment phase. Pre-assignment PK Day, each subject has baseline PK urine samples collected immediately prior to ferric maltol dosing (0 h). Following this, subjects will take a single dose of 0.1 ml/kg ferric maltol under supervision. Three (3) PK urine samples will be taken between 0.5 hr -3 hrs, 3 hrs -6 hrs, and 7 hrs -12 hrs post dose. N.B: samples should be taken at least 1.0 h apart. Urine collections instructions are detailed in the study's Laboratory Manual.

PK Day 2 (Visit 3), each subject has baseline PK blood and urine samples collected immediately prior to ferric maltol dosing (0 h). Following this, subjects will take a single dose of 0.1 ml/kg ferric maltol under supervision. Three PK Post-dose blood samples will be collected at the following windows 1.0-2.0 hrs, 3.0-4.0 hrs and 10.0-12.0 hrs; post-dose urine samples will be taken between 0.5 hr -3 hrs, 3 hrs -6 hrs and 7 hrs -12hrs post dose.

In the event of an administered dose not being consumed or partially consumed by the patient this will be noted as a missed dose and will not be repeated.

- 7. Eligibility laboratory sampling/assessments must be completed before the subject is assigned to ferric maltol. The PK samples will be analysed and if evidence of metabolism and elimination of maltol is shown, these subjects will enter the ferric maltol treatment phase Visit 2.
- 8. Subjects who have at least one dose of study medication and withdraw early from the study undergo Visit 7 (Day 94-98) assessments (excluding those who have withdrawn consent).
- 9. Visit 7 is conducted by telephone, unless the subject has an ongoing AE that requires physical examination or investigations for assessment/management. Visit 7 will take place 10-14 days after Visit 6 (Week 12) unless subject discontinued treatment early. All withdrawn subjects should undergo Visit 7 within 10-14 days after the last dose of study drug (if the subject agrees in the case of withdrawn consent).
- 10. Visit Windows: Maximum of 28 days between screening and pre-assignment phase. The Subject must visit to complete:
 - a. Visit 3: must be 7-10 days from Visit 2
 - b. Visit 4: +/- 5 days relative to date of Visit 2/first dose administered
 - c. Visits 5 to 6: +/- 5 days relative to date of Visit 2/first dose administered

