11.2 REPORTING AND DOCUMENTATION

AEs should be documented in terms of a medical diagnosis. When this is not possible, the AE should be documented in terms of signs and/or symptoms observed by the Investigator or reported by the subject at each study visit.

Any pre-existing conditions or signs and/or symptoms present in a subject prior to the start of the study should be recorded on the Medical History CRF.

All SAEs that occur after informed consent through to study completion (Follow-up visit) or premature discontinuation must be reported on the SAE form in the CRF and reported within 24 hours to the Sponsor using the Shield SAE form. All AEs occurring from the time of the first dose of study treatment through study completion (Follow-up visit) or premature

CONFIDENTIAL Page 67 of 80

discontinuation must be reported on the AE form in the CRF. For AEs related to COVID-19 testing, see section 10.1.

Any SAE that occurs during the clinical study or within two weeks of receiving the last dose of study drug, whether or not related to the study drug, must be reported to the Sponsor.

Deaths or congenital abnormalities if brought to the attention of the Investigator AT ANY TIME after cessation of study drug AND considered by the Investigator to be possibly related to study drug, should be reported to the Sponsor.

At each visit AEs will be solicited. The nature of each event should be established. Details of changes to study drug dosing or any subsequent treatment should be recorded on the appropriate pages of the CRF.

AEs already documented in the CRF (i.e., at a previous assessment) and designated as 'ongoing' should be reviewed at subsequent visits as necessary. Upon resolution, the date of resolution should be recorded in the CRF. If an AE increases in frequency or severity during a study period, a new record of the event should be started. If the AE lessens in intensity, no change in the intensity is required as only the worst intensity must be reported.

All AEs and SAEs, including those that are ongoing at the end of the study or at premature discontinuation, will be followed up until resolution or stabilisation or until the event is otherwise explained.

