12.3.2 Safety Population

All subjects who have had at least one dose of study drug will be analysed for safety.

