12.3.4 Pharmacokinetic (PK) Population (Full Analysis Set)

All subjects who have had at least one dose of study drug and who have at least one evaluable post-dose PK sample (applicable only for ferric maltol group) will be included in the PK analysis.

CONFIDENTIAL Page 73 of 80

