3.2.3 Safety Population

The Safety Population is defined as all randomised/assigned subjects who receive at least one dose of study drug. All safety data will be analyzed using the Safety Population.

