3.2.4 Pharmacokinetic (PK) Population (Full Analysis Set)

The PK Population is defined as all randomised/assigned subjects who have had at least one dose of study drug and who have at least one evaluable post-dose PK sample (applicable only for ferric maltol group). All PK data will be analyzed using the PK population.

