4.3 Final Analysis

After all comments on the pre-final analysis have been resolved and the study database is declared final, the final analysis will be generated. Final TFLs will be provided approximately 1 week after the study database is declared final. If there were no changes to the pre-final analysis or the study database, the pre-final TFLs may be considered final. In addition to TFLs, SDTM (study data tabulation model) data and ADaM data along with associated files will be provided. Associated files may include: annotated CRFs, SDTM specifications, SDTM programs, ADaM specifications, ADaM programs, TFL programs, and CDISC (Clinical Data Interchange Standards Consortium) Define packages for both SDTM and ADaM data.

5 CHANGES FROM PROTOCOL-SPECIFIED STATISTICAL ANALYSES.

The primary analysis for change in Hb is based on mITT, and additional sensitivity analyses will be based on the ITT and PP population.

The addition of changes in iron markers from baseline to Week 4 as a secondary endpoint deviates from the secondary endpoints listed in section 6.4 of the protocol.

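### The SAP limits the Safety and PK Populations to randomised or assigned subjects, so an infant dosed at pre-assignment but never assigned would be missing from the AE tables and the pre-assignment urine concentration summary

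*SAP*

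**What the plan says.** On safety, Protocol 12.3.2 reads: "All subjects who have had at least one dose of study drug will be analysed for safety". SAP 3.2.3 reads: "The Safety Population is defined as all randomised/assigned subjects who receive at least one dose of study drug", and sends all safety data through that set.

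On PK, Protocol 12.3.4 includes "All subjects who have had at least one dose of study drug and who have at least one evaluable post-dose PK sample". SAP 3.2.4 begins: "The PK Population is defined as all randomised/assigned subjects who have had at least one dose of study drug". It then asks for the same evaluable sample and sends all PK data through that set. Both PK definitions carry a note limiting them to the ferric maltol group.

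SAP section 5, which lists departures from the protocol analyses, has two entries. One is on populations, and it concerns haemoglobin only: "The primary analysis for change in Hb is based on mITT, and additional sensitivity analyses will be based on the ITT and PP population". The other adds Week 4 iron markers. Neither mentions the Safety or PK Population.

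For the infants, Protocol 10.4 note 6 says: "All subjects in 1 m-< 2 yrs age group will enter a 1-day PK assessment day prior to entering the treatment phase". The schedule in 10.4 marks adverse events and urine PK at that pre-assignment visit, and marks treatment assignment only at Visit 2. Protocol 9.2 has the samples reviewed infant by infant, and adds: "The investigator will make the final decision if subjects aged 1 month to < 2 years are eligible to enter the treatment phase". Protocol 11.2 starts AE reporting at the first dose: "All AEs occurring from the time of the first dose of study treatment through study completion (Follow-up visit").

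**The concern.** In ages 2 to 17, randomisation comes before the first dose, so the added condition removes no dosed subject. In infants the order is reversed: dose first, assignment later and conditional. The SAP wording therefore removes any infant who took the single dose and then was not assigned, whether because of the maltol result, an adverse event, the investigator's decision or withdrawal.

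Two summaries are exposed. The first is the set of AE incidence tables in SAP 3.6, which serve a primary endpoint and, for infants, part of the first primary objective. The second is the urine concentration summary in SAP 3.5.3 for the pre-assignment day. If the reason for non-assignment is that maltol elimination was not shown, the urine summary would contain only infants who passed the check, although the pre-assignment phase exists to find out whether infants eliminate maltol.

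**Working it through.** The plan gives no figure to reproduce here and no expected rate of non-assignment. The check is a comparison of definitions followed by a count.

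**Step 1: who is in each set.** Take an infant with a pre-assignment dose, post-dose urine samples and no Visit 2 assignment.

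- Protocol Safety Population: dosed, so included.
- SAP Safety Population: dosed but not assigned, so excluded.
- Protocol PK Population: dosed, with an evaluable post-dose sample, so included.
- SAP PK Population: not assigned, so excluded.

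**Step 2: can such an infant exist?** Yes. Assignment depends on the individual PK review (Protocol 9.2), and Protocol 7.5 provides for infants who do not enter the treatment phase when there is any sign of accumulation.

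**Step 3: size in the AE tables.** SAP 3.6 summarises by treatment received and specifies no age split for AEs, so the planned output is a pooled ferric maltol column. Inputs: 49 subjects aged 2 to 17 in the ferric maltol arm and a maximum of 12 infants (Protocol synopsis and 7.1). If all are dosed, the protocol denominator is 49 + 12 = 61. With one unassigned infant, the SAP denominator is 60.

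Let a be the number of the other 60 subjects who have a given event. If the omitted infant also had it, the shift is

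(a + 1)/61 − a/60 = (60 − a)/3660.

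- a = 0: 1/61 = 1.6% becomes 0/60 = 0%, a shift of 1.64 points. Exact 95% limits are 0.04% to 8.8% for 1/61, and an upper limit of 6.0% for 0/60.
- a = 10: 1.37 points.
- a = 20: 21/61 = 34.4% becomes 20/60 = 33.3%, a shift of 1.09 points.
- a = 40: 0.55 points.

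If the omitted infant did not have the event, the shift is a/61 − a/60 = −a/3660, which is also at most 1.64 points in size. One omitted infant therefore moves a pooled incidence by no more than 1/61, about 1.6 points.

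**Step 4: size in the urine summary.** With 12 infants dosed and one not assigned, n is 11 instead of 12. Suppose instead that the k-th dosed infant fails the check, the cohort is suspended under Protocol 7.5 and no later infant is dosed. The summary then holds k − 1 of k infants (11 of 12, 5 of 6, or 0 of 1), and the missing infant is the one who failed.

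**The case against.** **The protocol's PK set may already depend on group membership.** Its note restricts it to the ferric maltol group, and infants join that arm only after passing the check. The more natural reading is that the note excludes ferrous sulfate subjects, who have no PK sampling. The SAP keeps the same note and adds the assignment condition on top of it, so the added words still narrow the set.

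**Assigned might be meant to cover the pre-assignment dose.** The schedules in both documents place treatment assignment at Visit 2 only, as a separate step after the PK result, so this reading does not fit.

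**The data are not lost.** This stands. SAP section 6 lists all available data, SAP 3.3.1 accounts for all screened subjects, and Protocol 11.2 requires SAE reporting whatever the analysis population. What goes missing is a place in the summary tables.

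**The serious route has its own control.** This also stands. Any sign of accumulation suspends recruitment to the age group until the risk is assessed and a substantial amendment approved (Protocol 7.5). Some infants could then be assigned later.

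**The urine summary may not be produced.** SAP 3.5.3 allows listings only when an age group has too little data. If that is invoked, there is no urine summary to distort.

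**Conclusion.** The SAP departs from the protocol on both populations without declaring it, and the rule as written can exclude an infant because of the result being summarised. It should be corrected, but the consequence is limited. It needs at least one infant dosed and not assigned, and the documents give no expected number. It concerns at most 12 infants, in a cohort the study may be completed without (Protocol 12.1). Per omitted infant, the pooled ferric maltol incidence moves by at most about 1.6 points, assuming planned recruitment and everyone dosed. If every dosed infant is assigned, population membership does not change.

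A reader might infer more than the documents support:

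- That a safety signal would be hidden. The listings, SAE reporting and suspension rule prevent that conclusion.
- That infant incidence would read 0/11 (exact upper limit 28.5%) instead of 1/12 (8.3%, 0.2% to 38.5%). The arithmetic is right, but the SAP plans no infant-only AE table.
- That this wording explains why the infant urine amounts and renal clearance named in Protocol 12.2.2 are not planned. They are absent because SAP 3.5.4 plans PK parameters for ages 2 to 17 only, which is a separate gap.
- That the main comparisons are affected. The safety comparison within ages 2 to 17 is not, because dosing follows randomisation there. The haemoglobin analysis uses other populations.

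**What to change.** 1. Delete the randomised/assigned condition from SAP 3.2.3 and 3.2.4, so that they match Protocol 12.3.2 and 12.3.4.
2. State in SAP 3.6.1 that the first dose of study drug, for defining TEAEs, includes the pre-assignment dose. This is useful even if every infant is assigned, because SAP 3.1.1 and 3.3.8 count from the first treatment-phase dose.
3. Show pre-assignment-only infants as a separate group in the AE and urine concentration summaries, so that single-dose exposure is not mixed with 12-week exposure. Identify them by a recorded pre-assignment dose with no Visit 2 assignment. The exposure split in SAP 3.3.8 will not serve, because it marks every infant dosed at pre-assignment.
4. Align the first-dose date in SAP 3.1.1 and 3.3.8, which is undefined for an infant who never starts the treatment phase. Align also the denominator in SAP 3.3.3, which is all randomised/assigned subjects and could otherwise be smaller than the Safety Population.

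The cost is SAP wording, one derived flag and minor table changes. No new data are needed.

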3.2.4 Pharmacokinetic (PK) Population (Full Analysis Set)

The PK Population is defined as all randomised/assigned subjects who have had at least one dose of study drug and who have at least one evaluable post-dose PK sample (applicable only for ferric maltol group). All PK data will be analyzed using the PK population.

3.3 Subject Data and Study Conduct

3.3.1 Subject Disposition

Counts and percentages of subjects who were screened (signed informed consent), discontinued early during screening (screen failures), and randomised/assigned will be summarised in total based on all screened subjects. Reasons for early discontinuation will also be summarised.

Counts and percentages of subjects who were randomised/assigned, discontinued early from the study, and completed the study will be summarised by treatment and in total based on all randomised subjects. Reasons for early discontinuation will also be summarised.

3.3.2 Protocol Deviations

Counts and percentages of subjects with CSR reportable protocol deviations by deviation category will be summarised by treatment and in total based on all randomised/assigned subjects.

3.3.3 Analysis Populations

Counts and percentages of subjects in each analysis population will be summarised by treatment and in total based on all randomised/assigned subjects.

3.3.4 Demographic and Baseline Characteristics

The following demographic and baseline characteristics will be summarised:

- Age (years) and age categories (1 month to <2 years, 2 years to 9 years, 10 years to 17 years),
- Sex,
- Childbearing potential, if Female or Undifferentiated,
- Race.
- Ethnicity,
- Height/Length (cm),
- Weight

Body mass index (BMI) (kg/m²).

Demographic and baseline characteristics will be summarised with descriptive statistics or counts and percentages of subjects as appropriate by treatment and in total for all randomised/assigned subjects split by age categories of 1 month to 2 years and 2 years to 17 years.

3.3.5 Medical History

Medical history will be coded to system organ class and preferred term using the Medical Dictionary for Regulatory Activities (MedDRA) version 24.0. Counts and percentages of subjects with medical history by system organ class and preferred term will be summarised by treatment and in total based on all randomised/assigned subjects. This will also be displayed for those patients in the 1 month to 2 years, 2 years to 9 years and 10 years to 17 years age group.

3.3.6 Concomitant Medications

Concomitant medications will be coded to anatomical therapeutic chemical (ATC) class and preferred term using the WHODrug Dictionary version B3 Global, March 2021. For summary purposes, medications will be considered prior medications if they were taken within 3 months prior to the first dose of study drug and concomitant medications if they were taken at any time after the first dose of study drug (i.e. started prior to the first dose of study drug and were ongoing or started after the first dose of study drug).

If a medication has incomplete start or stop dates, dates will be imputed to determine whether a medication should be considered prior or concomitant. If a medication start date is incomplete, the first day of the month will be imputed for missing day and January will be imputed for missing month. If a medication stop date is incomplete, the last day of the month will be imputed for missing day and December will be imputed for missing month. Incomplete start and stop dates will be listed as collected without imputation.

Counts and percentages of subjects taking prior and concomitant medications by ATC class and preferred term will be summarised by treatment and in total based on the Safety Population. This will also be displayed for those patients in the 1 month to 2 years, 2 years to 9 years and 10 years to 17 years age group.

3.3.7 Concomitant Procedures

Concomitant procedures will be coded to class and standardised procedure name using MedDRA version 24.0. For summary purposes, procedures will be considered prior procedures if they took place within 3 months prior to the first dose of study drug and concomitant procedures if they took place at any time after the first dose of study drug (i.e. started prior to the first dose of study drug and were ongoing or started after the first dose of study drug).

If a procedure has incomplete start or stop dates, dates will be imputed to determine whether a procedure should be considered prior or concomitant. If a procedure start date is incomplete, the first day of the month will be imputed for missing day and January will be imputed for missing month. If a procedure stop date is incomplete, the last day of the month will be imputed for missing day and December will be imputed for missing month. Incomplete start and stop dates will be listed as collected without imputation.

Counts and percentages of subjects who had prior and concomitant procedures by class and standardised procedure name will be summarised by treatment and in total based on the Safety Population.

3.3.8 Study Drug Exposure and Compliance

Days of exposure to study drug will be calculated as date of last dose of study drug – date of first dose of study drug + 1. For subjects who received a dose during the pre-screening period the date of first dose will be the date of first dose in the treatment phase. Note that the exposure calculation is intended to describe the length of time a subject was exposed to study drug and therefore does not take study drug interruptions into account. Days of exposure to study drug will be summarised by treatment based on the Safety Population with descriptive statistics and with counts and percentages of subjects with exposure in the following categories:

- <=6 days,
- 7 27 days,
- 28 55 days,
- 56 83 days,
- >= 84 days.

Days of exposure to study drug will be summarised separately for those who received a dose in the pre-assignment phase and those who didn't.

Percent compliance to the study drug regimen will be calculated as 100 x doses taken/ doses expected as recorded in dosing diary. Percent compliance to the study drug regimen will be summarised by treatment based on the Safety Population with descriptive statistics and with counts and percentages of subjects with compliance in the following categories:

- <80%,
- 80-120%,
- >120%.

